8.1.3 Site Covariate

For the purposes of modeling and imputation, all sites with less than 10 patients will be pooled into a single large site. In listings and analyses by site, patients will appear under their study site identifier (not the pooled site).

8.1.4 Imputation of Missing Data

For individual daily pain scores, since a mean is used in the calculation of the primary endpoint, it is not necessary to replace values missing on random intermittent days; weeks will have average values as long as a single value for that week is present.

Daily sleep diary data will be handled in an identical manner to the pain scores.

Continuous outcomes included in the list of key secondary outcomes that are collected in-clinic will be handled as above, minus the step of creating weekly averages of daily values and with steps being done by visit instead of week.

Patients with missing PGIC at a given visit will be considered non-responders at that visit for the purposes of treatment comparisons and efficacy claims; additional tabulations will summarize the number and percentage in each category out of non-missing values as well as a count of the missing values.

No missing safety data will be imputed.

Protocol: TNX-CY-F307 Page 20 of 45

Final v1.0

8.2 Efficacy Assessments

8.2.1 Average Daily Pain Score

The average daily pain score will be obtained using the daily, 24-hour recall, NRS pain data collected with the diary system. Since a mean is used in the calculation of the primary endpoint, it is not necessary to replace values missing on random intermittent days.

The baseline pain score will be defined as the average of the pain scores from the 7 days prior to the baseline visit. Pain scores must be recorded on at least 5 out of the 7 days immediately preceding the baseline visit in order for the patient to qualify for randomization.

The mean of the daily, patient self-reported, 24-hour recall, pain severity scores for the 7 days of each week will serve as the pain score for that study week. All available values will be used; if a patient has at least one value for the week, the week is non-missing. Because there is a -4 day and +7 day window around the scheduling of Visit 6 (Day 99), the study weeks will be anchored by the timing and completeness of their final study visit. Ideally, patients appearing in-clinic on Day 99 (defining randomization as Day 1), would have last filled out their diary on Day 98; therefore, "Week 14" would include Days 92-98; the protocol-defined window allows visit 6 as early as Day 95, resulting in a nominal "Week 14" including Days 88-94. Likewise, patients may appear in-clinic per protocol as late as Day 106, resulting in a "Week 14" interval running from Day 99-105.

Due to impacts from the COVID-19 pandemic, the criteria for calculating the Week 14 average will be marginally relaxed beyond the protocol-specified visit windows to allow for additional flexibility by permitting data collected during Week 13 to be used to calculate the Week 14 average: working backwards from Day 98, the first non-missing day (as early as Day 91) will serve as the LAST day of Week 14 for the purpose of anchoring and any non-missing values in the 6 days prior to that day will contribute to the average. If a patient does not have a non-missing value on/after Day 91, any available data from Day 85-91 will be averaged as Week 14 and Day 91 will serve as the anchor. Patients without data on/after Day 85 will be missing for Week 14 and handled as described below. Specific examples of calculating the Week 14 pain score are described in Appendix C.

Each week prior to Week 14 will be based on 7-day intervals; depending on the interval selected for "Week 14", this will result in Week 1 having less than 7 days or some "extra" days prior to Week 1. Extra days will be dropped and not included in the analysis; in the case of less than 7 days, the available days will be averaged, as long as there are non-missing values. The earliest day included in the Week 1 average will be the data entered the day after randomization (covering roughly the 24 hours following their first dose of study drug).

For patients who withdraw from the study early, that do not have a final study visit or complete the study but do not have data in the 7 days preceding their last visit, the last day of diary data (at or prior to Day 106) will serve as the anchor point for dividing the available data into weeks. First, the nearest nominal end day for a weekly period is identified and this week will be the assigned the data from the 7 days immediately preceding the anchor date. For example, if a patient early terminates on study Day 24, the Week 3 (nominally ending on day 21) average will be based on the 7 days prior to Day 24 (Days 17-23). Lost to follow-up patients that continue to fill out the diary into Week 14 and beyond will have non-missing values for the Week 14

Protocol: TNX-CY-F307 Page 21 of 45

Final v1.0

timepoint for diary outcomes. Day 106 will be the last allowable day to be included in the average.

	Nominal Study
Week	Day Intervals
Baseline	Day -7 to -1
Day of	
Randomization	Day 1
Week 1	Day 2 to 7
Week 2	Day 8 to 14
Week 3	Day 15 to 21
Week 4	Day 22 to 28
Week 5	Day 29 to 35
Week 6	Day 36 to 42
Week 7	Day 43 to 49
Week 8	Day 50 to 56
Week 9	Day 57 to 63
Week 10	Day 64 to 70
Week 11	Day 71 to 77
Week 12	Day 78 to 84
Week 13	Day 85 to 91
Week 14	Day 92 to 98

Change from baseline will be defined as the pain score at each week minus the baseline pain score (with baseline and weekly pain scores derived as described above). Thus, negative changes will denote lesser pain and larger negative values will denote greater improvement.

8.2.2 Average Daily Sleep Quality Score

The average daily sleep quality score will be obtained in the same manner as the average daily pain score, via electronic Interactive Response Technology (IRT) system. Derivation of the weekly average sleep quality scores and censoring of data will be treated the same as the weekly average pain scores described in Section 8.2.1, using the same windows based on the date of collection. It should be noted that the sleep prompt asks about the prior night's sleep; thus, patients report their sleep starting the first night that they take randomized drug through the night between day 97-98, if their final visit is day 99. As with pain, negative changes will denote improvement in sleep quality and larger negative values will denote greater improvement.

8.2.3 Patient Global Impression of Change (PGIC)

PGIC is a question completed by the patient at Weeks 2, 6, 10, and 14. The patient will rate the change in their overall fibromyalgia symptoms on a 1-7 Likert scale, where 1 is "Very Much Improved" and 2 is "Much Improved". Scores of 1 and 2 will be considered PGIC responders, and all other scores will be considered non-responders for that visit. The proportion of responders in each treatment arm will be analyzed. Any missing PGIC score will be considered a non-responder for that visit.

Protocol: TNX-CY-F307 Page 22 of 45

Final v1.0

An exploratory analysis will include "Minimally Improved" (3) as responders, in addition to scores of 1 and 2.

8.2.4 Revised Fibromyalgia Impact Questionnaire (FIQR)

The FIQR is made up of 3 domains: (1) functional (9 questions); (2) overall impact (2 questions) and (3) symptoms (10 questions). If 2 or more items are missing from the functional domain, the domain will be considered invalid for that visit. Likewise, if *any* item is missing from the overall impact domain or the symptom domain, those domains will be considered invalid.

To account for missing items in the functional domain, the score will be recalculated as:

New score = (Raw score / # of items answered) \times # of items in domain

The FIQR total score can be determined after all domain scores have been calculated using the following steps. First, divide the function domain score by 3, divide the overall impact domain score by 1, and divide the symptom domain score by 2. Next, add the three resulting domain scores to obtain the total score of FIQR. If any domain score is missing, then the total is missing.

8.2.5 Patient Reported Outcomes Measurement System (PROMIS) Instruments

8.2.5.1 PROMIS Short-Form (SF) Fatigue and Sleep Disturbance Instruments

The PROMIS Short-Form Fatigue and Sleep Disturbance Instruments each consist of 8 items in which responses are scored 1 to 5 for each item. Scores for all items are totaled to create a raw score. Either instrument will be considered invalid if 50% of the items are missing. If more than 50% of the items are answered, the raw total score will use the following formula to determine a new calculated score to account for missing items.

New raw score = (Raw score / # of items answered) \times # of total items

New raw scores that are fractions are rounded up to the nearest whole number. Once a new raw score has been calculated, a T-score will be determined using Appendix A for Fatigue Inventory and Appendix B for Sleep Disturbance. The T-scores will be analyzed.

Note that items 1, 2, and 8 of the PROMIS Sleep Disturbance Instrument will need to have their directionality reversed for calculating the totals.

8.2.6 Changes in Sexual Functioning Questionnaire Short-Form (CSFQ-14)

The CSFQ-14 (Keller et al. 2006) is a validated scale with internal reliability designed to allow a patient to self-evaluate his or her sexual behaviors or problems in a number of areas. The CSFQ-14 will be administered at Baseline (Visit 2) and Week 14/ET (Visit 6). It yields a total score, three subscales corresponding to phases of the sexual response cycle (i.e. desire, arousal, orgasm), and five subscales corresponding to important dimensions of sexual functioning. It is considered a useful scale for assessing sexual side effects of medications. For all items, higher scores reflect higher sexual functioning. For 12 of the 14 items, higher sexual functioning corresponds to greater frequency or enjoyment/pleasure (e.g. 1=never to 5 = every day). For two items (item 10, assessing loss of interest after arousal for women and priapism for men, and item

Protocol: TNX-CY-F307 Page 23 of 45

Final v1.0

14, assessing painful orgasm), higher sexual functioning corresponds to lower frequency (e.g. 1=every day; 5=never). Items 10 and 14 are included in the total score but not in any subscale scores.

8.3 Safety Endpoints

To handle missing or partial AE and concomitant medication dates, the following rules will be applied.

For partial start dates:

- 1. If the year is unknown, then do not impute the date but assign a missing value.
- 2. If the month is unknown, then:
 - a. If the year matches the year of the first dose date, then impute the month and day of the first dose date.
 - b. Otherwise, assign "January."
- 3. If the day is unknown, then:
 - a. If the month and year match the month and year of the first dose date, then impute the day of the first dose date.
 - b. Otherwise, assign "01."

For partial end dates:

- 1. If the year is unknown, then do not impute the date but assign a missing value.
- 2. If the month is unknown, then assign "December."
- 3. If the day is unknown, then assign the last day of the month.

Adverse events are categorized as pre-treatment adverse events or treatment-emergent adverse events based on the response to the CRF question "Did the AE start prior to the first dose?"

The missing severity of an AE will be imputed to "severe"; the missing relationship to study drug of an AE will be imputed to "possibly related".

After implementing the rules above, the following strategy will be used to determine whether medications with missing start or stop dates are prior or concomitant medications:

- 1. If the start date and stop date are both missing, then the most conservative approach is taken and the medication is considered to be a concomitant treatment.
- 2. If the start date is missing but the stop date is not missing and is after the day of first study dose administration, then the most conservative approach is taken and the medication is considered to be concomitant.
- 3. If the start date is missing but the stop date is not missing and is on or before the day of first study dose and after the date of signed informed consent, then the medication is considered to be a prior treatment.
- 4. If the start date is not missing but the stop date is missing, then the most conservative

Protocol: TNX-CY-F307 Page 24 of 45

Final v1.0

approach is taken and the medication is considered to be concomitant.

Protocol: TNX-CY-F307 Page 25 of 45

Final v1.0

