12.3.1. Adverse Events

Patients will be monitored for AEs throughout the study. Any clinically significant abnormal findings at screening should be recorded in medical history. Adverse Events will be recorded after the informed consent is signed. AEs that are spontaneously reported or elicited or observed are to be recorded on the CRF with the date, time of onset, date and time of resolution, severity, seriousness, causality (relationship to study drug), actions required, and outcome. Additional questions will be triggered for AEs involving the oral cavity.

To elicit AEs, non-leading, simple questions with minimal connotations should be used as the initial questions at all evaluation points during the study. Examples of these questions can be:

- How have you felt since your last visit?
- Have you had any health problems since your last visit?

If an AE occurs, the Investigator will institute support and/or treatment as deemed appropriate. If an AE is unresolved on the last day of the study, an effort should be made to follow up until the AE is resolved or stabilized, the patient is lost to follow-up, or there is some other resolution of the event.

There are many symptoms associated with fibromyalgia that can vary in intensity and frequency over time. Only symptoms that worsen or become more frequent, and in the opinion of the patient are outside of their normal experience, should be reported as adverse events.

Additional information regarding definition and reporting requirements for adverse events, serious adverse events, and pregnancies is provided in Section 14.

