14. DEFINITIONS, RECORDING, AND REPORTING OF ADVERSE EVENTS

14.1. Definition of Adverse Events

According to International Council for Harmonisation (ICH) guidance E2A, Clinical Safety Data Management: Definitions and Standards for Expedited Reporting, an AE is any untoward medical occurrence in a patient or clinical investigation subject administered a pharmaceutical product and which is not necessarily required to have a causal relationship with this treatment. An AE can therefore be any unfavorable and unintended sign (including an abnormal laboratory finding, for example), symptom, or disease temporally associated with the use of a medicinal product, whether or not considered related to the medicinal product.

A TEAE is an AE that either commenced following initiation of study treatment or was present prior to study treatment but increased in frequency or severity following initiation of study treatment.

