11.1 Adverse Events

All AEs, TEAEs, and SAEs will be coded using the MedDRA Dictionary Version 23.0.

The collection of adverse events will begin at the time the patient is consented and screened for the study. Treatment-emergent adverse events (TEAEs) are defined as either new onset AEs with an onset at the time of or following the start of treatment, as indicated by a "no" answer to "Did AE start prior to the first dose?", or a recurrence of an AE (or medical history) present prior to randomization but increasing in severity, frequency or relationship at the time of or following the start of treatment.

An AE summary table will be presented for the following:

- All TEAEs
- TEAEs by severity
- TEAEs leading to study drug discontinuation
- TEAEs by relationship
- SAEs
- Oral cavity TEAEs
- Oral cavity TEAEs by severity

Summaries of incidence rates (frequencies and percentages), of individual AEs by MedDRA SOC and preferred term will be prepared. Such summaries will be displayed for all TEAEs, oral cavity TEAEs, TEAEs by maximum severity, TEAEs by strongest relationship to study drug and post-treatment AEs.

Each patient will be counted only once within each summation level (SOC; preferred term). If a patient experiences more than one TEAE within each summation level, the TEAE with the strongest relationship or the maximum severity, as appropriate, will be included in the summaries of relationship and severity.

In the AE data listings, all AEs will be displayed. AEs that occur prior to randomization will be considered pre-treatment AEs, and will be determined by a "yes" response to the CRF question, "Did the AE start prior to the first dose?" AEs that start on the date of randomization but have a "yes" response to this question will be categorized as pre-treatment AEs. TEAEs will be defined

Protocol: TNX-CY-F307 Page 32 of 45

Final v1.0

from the date of randomization and a "no" response to the CRF question, "Did the AE start prior to the first dose?"

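### The AE sorting rule in SAP 8.3 and at the end of SAP 11.1 has no exception for worsening, which contradicts the TEAE definitions in Protocol 14.1 and the opening of SAP 11.1

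*SAP*

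**What the plan says.** The plan gives two definitions of a TEAE and two statements of a sorting rule.

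**Definitions**
- Protocol 14.1: besides new-onset events, a TEAE is an AE that "was present prior to study treatment but increased in frequency or severity following initiation of study treatment".
- SAP 11.1, second paragraph: besides new-onset events (shown by a 'no' answer to the CRF question), a TEAE is "a recurrence of an AE (or medical history) present prior to randomization but increasing in severity, frequency or relationship" once treatment has started.

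**Sorting rule**
- SAP 8.3: "Adverse events are categorized as pre-treatment adverse events or treatment-emergent adverse events based on the response to the CRF question" on whether the event started before first dose.
- SAP 11.1, last paragraph: "AEs that occur prior to randomization will be considered pre-treatment AEs", as shown by a 'yes' answer to that question. TEAEs are those "from the date of randomization and a 'no' response to the CRF question".

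Protocol 12.3.1 fixes when collection starts: "Adverse Events will be recorded after the informed consent is signed". Pre-dose events can therefore be on file at randomization.

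**The concern.** A pre-dose AE that becomes worse on drug still began before the first dose, so the CRF question must be answered 'yes'. The definitions make that event a TEAE, and the sorting rule makes it pre-treatment. A programmer who follows the rule and one who follows the definition would produce different TEAE tables from the same data.

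Safety is the trial's secondary objective, and the between-arm AE comparison rests on the TEAE tables. The situation is realistic. Screening normally lasts 1 to 5 weeks (Protocol 7.3), can reach 49 days with approval (Protocol 7.1), and may include withdrawal of excluded medicines. The SAP itself expects pre-treatment AEs, since SAP 11.1.3 plans to list them for the oral cavity. SAP 13 records only the added continuous PGIC analysis as a change, so it declares no departure from Protocol 14.1.

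**Working it through.** No figure is at stake, so the check is to run each kind of event through the definitions and the rule.

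| Case | Protocol 14.1 and SAP 11.1 opening | CRF answer | SAP 8.3 and SAP 11.1 closing rule |
|---|---|---|---|
| (a) AE starts after first dose | TEAE | no | TEAE |
| (b) AE starts between consent and first dose, does not worsen | not a TEAE | yes | pre-treatment |
| (c) As (b), but worsens on treatment and is kept as one record | TEAE | yes | pre-treatment |
| (d) As (c), but the worsening is entered as a new AE | TEAE | no, if dated from the worsening | TEAE |
| (e) Baseline fibromyalgia symptom, first reported as an AE when it worsens on treatment | TEAE | naturally no | TEAE |

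The conflict is confined to case (c).

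**Can case (c) occur as one record?** Protocol 12.3.1 asks for onset, resolution, severity, seriousness, causality, actions and outcome. It does not ask for a date of severity change. Neither document tells sites to open a new record when an AE already on file gets worse. So (c) and (d) are both possible, and site practice decides between them.

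**Why (e) mostly escapes.** For the symptoms of fibromyalgia, Protocol 12.3.1 says "Only symptoms that worsen or become more frequent", and that the patient regards as outside normal experience, are reported as AEs. The reportable event is the worsening, so an on-treatment worsening would naturally be dated on treatment. The exception is a symptom already reported as an AE during screening that worsens further on drug, which returns to (c) or (d).

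**Where a case (c) event goes under the rule**
- SOC and preferred-term tables, which SAP 11.1 builds on TEAEs ("Such summaries will be displayed for all TEAEs, oral cavity TEAEs, TEAEs by maximum severity, TEAEs by strongest relationship to study drug"): excluded.
- Table of TEAEs leading to discontinuation of study drug (SAP 11.1.1): excluded. The accompanying listing covers AEs, so the event is retained there.
- General AE listing (SAP 11.1) and oral-cavity listing (SAP 11.1.3): retained.
- SAE incidence table (SAP 11.1.2): retained if serious, because that table is not limited to TEAEs.

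**Effect on counts.** SAP 11.1 counts each patient once per SOC or preferred term. A lost record lowers an incidence only if the patient has no other TEAE at that level. It can also lower the maximum severity or strongest relationship shown for a patient who is still counted.

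**The case against.** The best defence is that SAP 11.1 already contains the worsening limb and ties the CRF question to new-onset events only. SAP 8.3 mainly deals with missing and partial dates, so its sentence can be read as settling timing without imputed dates, not as repealing the definition. This has some force. A reader might infer that the SAP recognises only new-onset TEAEs, and the opening of SAP 11.1 shows that it does not. But the last paragraph of SAP 11.1 is not about dates. It states a complete rule for TEAEs without the limb, so the contradiction remains inside one section.

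A second defence is that sites may open a new record for each worsening. The CRF and its completion guide are not among the documents, and the word 'recurrence' in SAP 11.1 is compatible with that practice. It would rescue the event, but nothing in the documents requires it.

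A third defence is that other outputs pick up worsening: the listings, the SAE table, laboratory shift tables (SAP 11.2), C-SSRS (SAP 11.3) and BDI-II change (SAP 11.4). They limit the loss. Listings give no between-arm incidence, and the scales and laboratory tests cover only their own domains.

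A reader might also infer that worsening of baseline symptoms such as fatigue or poor sleep would be lost wholesale. Protocol 12.3.1 largely answers that, as case (e) shows.

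**Conclusion.** The contradiction is real and should be removed before unblinding. It is narrow. An event is lost only if it began between consent and first dose, worsened on treatment, was kept as one record, and was classified by the sorting rule and not by the definition.

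The documents give no count or rate for such events, so the size is unknown and could be zero. It would be zero if no pre-dose AE worsens, if sites always enter worsening as a new AE, or if the programmer applies the opening definition of SAP 11.1.

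A reader might infer that the rule hides harm in the active arm. The documents do not establish that. If pre-dose AEs worsen more often on drug than on placebo, the between-arm difference would be understated; if they worsen equally often, mainly the absolute rates would be. Nothing in the documents says which holds.

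The primary and key secondary efficacy analyses are unaffected.

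**What to change.** 1. In SAP 8.3 and the last paragraph of SAP 11.1, define a TEAE as an AE with a 'no' answer, or an AE with a 'yes' answer whose severity or frequency increased on or after the first dose.
2. State that a medical-history item that worsens on treatment is entered as a new AE with its onset at the worsening. The CRF question is put about AEs, and nothing shows that it is asked of medical-history items.
3. Align the opening definition in SAP 11.1 with Protocol 14.1. The SAP speaks of a recurrence and adds a change in relationship as a criterion; the protocol has neither.
4. State how worsening is captured, either as a new AE record or as a severity-change date, so that the definition can be programmed.

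The cost is a few SAP sentences, one derivation and one data-cleaning check of pre-dose AEs for worsening, all before unblinding.
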